5 STUDY DESIGN

5.1 Overall Design

The study design will be a double-blind randomized controlled trial with crossover. Treatment will be blinded to the subjects and investigators. Patients will be randomly

assigned two (2) weeks of the case or control topical cream and then crossover to the other cream for two (2) more weeks. Patients will apply the cream at their thumb basal joint twice daily for one (1) hour. The subjects will be advised to observe for physiologic changes, skin changes, or other adverse effects. If mild to severe drug-related adverse events are noticed, the creams will be removed immediately and appropriate care and observation will be taken. Each condition will last for two (2) weeks and then subjects will be contacted by the study coordinator to facilitate crossover into the other condition. This study will last one year from the beginning of subject recruitment to data analysis. Subjects will be enrolled in this study for approximately six (6) weeks from Screening until the final Study Visit.

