4 OBJECTIVES AND ENDPOINTS

Objectives	Endpoints
Primary	
To determine therapeutic potential of CDB as a topical	Hand Functional Assessment: Change from baseline in hand functional assessment including grip, appositional,

treatment for thumb basal joint arthritis.	
and oppositional pinch strength (kg); Kapandji score; and MP and IP range of motion.
 
Patient Reported Outcome Measures: Change from baseline in the PROMIS-29 (Patient-Reported Outcomes Measurement Information System) and PROMIS upper extremity tests. The PROMIS-29 is a free publicly available generic health related quality of life (HRQoL) measure consisting of indices of pain, pain interference, depression, anxiety, global function, and social interactions. The PROMIS upper extremity test utilizes item-response theory and Computer Adaptive Test to efficiently and precisely report patient symptoms and perceived function.

Secondary	
To determine the safety of treatment CBD.
 
Safety will be determined by evaluating:
 
 • The frequency and severity of adverse events from the beginning of treatment through the end of study participation. • Changes in skin appearance from baseline using standardized skin assessment tool (patient will be removed from study with a score ≥ 2) • Clinically significant change in CBC (baseline and weekly follow-up) • Clinically significant change in basic metabolic panel (i.e., BUN, creatinine, CO₂, Cl, K, Na, and glucose) (baseline and weekly follow-up) • Clinically significant change in hepatic function testing (i.e., serum transaminases [ALT/AST], total bilirubin, and alkaline phosphatase) (baseline and weekly follow-up) • Clinically significant change in vital sign assessments (i.e., heart rate and blood pressure) • Suicidal behavior and thoughts as a specific question using the Columbia-Suicide Severity Rating Scale (C-SSRS) at baseline and follow-up.

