5.2 Justification for Dose

Nitecka-Buchta *et al.* performed a double-blind randomized controlled trial of topical CBD for 60 total patients with myofascial pain. Topical application of 67 mg CBD – including other minor cannabinoids – was applied to masseter muscles twice daily for 14 days in the case group. Visual Analog Scores (VAS) were reduced from 5.6 on Day 0 to 1.7 on Day 14 (70.2% reduction) in the case group, versus 5.1 on Day 0 and 4.6 on Day 14 (9.8% reduction) in the control group ($p = 0.00$). (4)

Xu *et al.* performed a randomized controlled trial with cross-over for topical CBD treatment of 29 patients with symptomatic lower extremity neuropathy. Topical application of 250 mg of pure CBD (case arm) was applied up to four (4) times daily for four (4) weeks, and then patients switched to emu oil (control arm) with the same application for 4 weeks followed by cross-over. They showed a statistically significant reduction in Neuropathic Pain Scale scores for intense (5.11 to 4.02) ($p=0.009$) and sharp (4.01 to 3.09) ($p<0.001$) pain between case and control arms. (5)

No side effects or adverse events were noted in either clinical trial.

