7.2 Dosing and Administration

Subjects will be randomized to receive a total of 28mL of either 6.2 mg/mL of CBD with Shea butter or Shea butter alone placed within three (3) 10mL syringes. Subjects will be advised to apply 1 mL of the cream overlying their thumb basal joint dorsally twice daily, approximately every 12 hours. In the CBD condition, the cream will be formulated to deliver approximately 12.4 mg of purified CBD per day, whereas in the control condition the Shea butter will be utilized alone. The purified CBD is colorless and odorless to facilitate blinding.

The CBD with Shea Butter or Shea butter alone will be provided to subjects in 10 mL syringes without a needle, with a rubber topper. Subjects will be instructed to store the cream at room temperature. Subjects may dispense the cream from the syringe into a gloved hand. Gloves will be provided to the subject along with the investigational product. The cream will need to be applied to the base of the thumb until completely absorbed. Subjects should avoid water to the area for at least one hour.

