9 STUDY ASSESSMENTS AND PROCEDURES

9.1 Clinical Assessments

Hand Functional Assessment: Hand functional assessment will include grip, appositional, and oppositional pinch strength (kg); Kapandji score; and MP and IP range of motion. Assessments will be performed at Baseline and study Days 7, 14, 21, and 28.

Patient Reported Outcome Measures: The PROMIS-29 and PROMIS upper extremity tests will be collected. The PROMIS-29 is a free publicly available generic HRQoL measure consisting of indices of pain, pain interference, depression, anxiety, global function, and social interactions (Attachment 1, Appendix 14.4) Subjects will complete the measure at Baseline and study Days 7, 14, 21, and 28. The PROMIS upper extremity test utilizes item-response theory and Computer Adaptive Test to efficiently and precisely report patient symptoms and perceived function. Subjects will complete the measure in clinic using an iPad. The PROMIS upper extremity assessment is provided in Attachment 2 (Appendix 14.4). Subjects will complete the PROMIS assessment at Baseline and study Days 7, 14, 21, and 28.

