11 STATISTICAL CONSIDERATIONS

11.1 Statistical Hypotheses

Outcomes between the two groups will be compared and in a within-subject analysis will be performed given the crossover design. A descriptive analysis of the variables will be performed by calculating mean and standard deviation (SD), as appropriate, and absolute and percentage frequency. Differences between pre- and post-treatment scores (delta scores) will be assessed with the Wilcoxon signed-rank test. Correlations between delta scores and the variables considered [age, gender, body mass index (BMI), radiographic features] will be evaluated with the Spearman, Mann-Whitney, and Kruskal-Wallis tests. The significance threshold will be set at 0.05.

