14 APPENDICES

14.1 Schedule of Activities (SoA)

Visit	Visit 1 (Screening and Baseline)	Visit 2 (Baseline)	Visit 3	Visit 4	Visit 5	Visit 6	Visit 7
Study Day	-7 ¹	0	7 (+/- 1)	14 (+/- 1)	21 (+/- 1)	28 (+/- 1)	35 (+/- 1)
Informed Consent	X						
Review study eligibility	X						
Blood Draw ²	X ³						X
Urine Pregnancy Test (if applicable)	X	X					
Hand Functional Assessment		X	X	X	X	X	
Patient Reported Outcome Measures		X	X	X	X	X	
Physician Skin Monitoring		X	X	X	X	X	X
Columbia- Suicide Severity Rating Scale	X	X	X	X	X	X	X

¹ Screening may take place within one week of baseline visit to allow for results of bloodwork and pregnancy testing.

² Blood pregnancy test to be ordered during screening visit only.

³ Baseline blood testing (Hemoglobin and Platelet count, Creatinine, AST/ALT) will be obtained at the screening blood draw.

Monitor for somnolence and sedation			X	X	X	X	X
Study Medication Dispensed		X		X			
Diary dispensed		X		X			
Diary Review			X	X	X	X	X
Study Medication Collected			X	X	X	X	
Assessment of Adverse Events		X	X	X	X	X	X

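### Section 11.1 ties its signed-rank test of before/after changes to no CBD-versus-control contrast, period-2 reference or carryover rule, in a crossover without washout

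*Combined protocol and SAP*

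**What the plan says.** **Design.** Section 5.1: "Each condition will last for two (2) weeks and then subjects will be contacted by the study coordinator to facilitate crossover". Section 7.2 sets the supply for a condition: "Subjects will be randomized to receive a total of 28mL of either 6.2 mg/mL of CBD with Shea butter or Shea butter alone", at 1 mL twice daily. In the Schedule of Activities (14.1), the row "Study Medication Dispensed" is marked only at Days 0 and 14.

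**Endpoints and visits.** Section 4 defines the efficacy endpoints as changes, for example: "Change from baseline in the PROMIS-29 (Patient-Reported Outcomes Measurement Information System) and PROMIS upper extremity tests". Section 9.1: "Assessments will be performed at Baseline and study Days 7, 14, 21, and 28". The schedule gives the baseline label to Visits 1 and 2 (Days -7 and 0), not to Day 14.

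**Analysis.** Section 11.1 opens: "Outcomes between the two groups will be compared and in a within-subject analysis will be performed given the crossover design". The only test it then names for the delta scores is this: "Differences between pre- and post-treatment scores (delta scores) will be assessed with the Wilcoxon signed-rank test". It does not say which score is the before-treatment score in period 2, whether the test is applied to the CBD change alone or to a CBD-minus-control difference, or how period, sequence and carryover are handled.

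**The concern.** In a crossover without washout, the score at the switch is taken while the first cream is in use. Two choices therefore decide what the named test measures: the quantity it is applied to, and the reference score for period 2. Section 11.1 fixes neither. One choice gives a test with no control comparison, which credits any improvement over time or on the control cream to CBD. Another keeps the control comparison but changes the size of the effect being estimated. Left open, the choice could be made after the data are seen. Separately, a CBD effect that outlasts period 1 would shrink the crossover estimate, and the plan does not acknowledge this.

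**Working it through.** **Inputs.** Dispensing on Days 0 and 14 and final visit on Day 35 (14.1); 28 mL per condition at 2 mL a day (7.2); 40 subjects, 50% reduction, variance 0.25, 80% power (11.2); 1:1 allocation (11.2.1), taken as 20 per sequence; threshold 0.05 (11.1), taken as two-sided; control arm of the myofascial pain trial (5.2): "versus 5.1 on Day 0 and 4.6 on Day 14 (9.8% reduction) in the control group".

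**1. No gap.** 28 mL / 2 mL per day = 14 days. Screening to final visit is 7 + 14 + 14 + 7 = 42 days, the six weeks of Section 5.1. Nothing is left for a washout.

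**2. The plan's own figure.** Reading the 50% reduction as 0.5 and the SD as √0.25 = 0.5 (the scale is not stated), 2 × (1.96 + 0.84)² × 0.25 / 0.5² = 15.7, rounded up to 16. This matches Section 11.2, so the same scale is used below.

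**3. Model.** Let d be the true CBD-minus-control effect, p1 and p2 the changes from Day 0 to Days 14 and 28 that would occur regardless of CBD, and L the fraction of the CBD effect still present at Day 28 in those given CBD first. L is assumed to lie between 0 and 1, because the documents give no duration of effect. The full effect is assumed to be present at the end of the CBD period.

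| Sequence | Day 0 | Day 14 | Day 28 |
|---|---|---|---|
| CBD first | 0 | d + p1 | Ld + p2 |
| Control first | 0 | p1 | d + p2 |

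**4. Reading (a): test on the CBD change alone.** Averaged over sequences, the CBD change is d + (p1 + p2)/2 with a Day 0 reference. With a Day 14 reference in period 2 it is d + (p1 + p2 - p1)/2 = d + p2/2. Now set d = 0 and take the cited control change, (5.1 - 4.6)/5.1 = 9.8%, as 0.098.
- Recurring each period (p1 = 0.098, p2 = 0.196): mean change 0.147 (Day 0) or 0.098 (Day 14).
- Occurring once (p1 = p2 = 0.098): 0.098 (Day 0) or 0.049 (Day 14).

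Simulated rejection rates with no CBD effect (SD 0.5, normal scores, 5,000 to 6,000 runs; within-subject correlation 0, then 0.5):

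| Change unrelated to CBD | Day 14 reference | Day 0 reference |
|---|---|---|
| None | 5.1%, 5.0% | 4.9%, 5.4% |
| 0.098 once | 6.8%, 9.3% | 14.2%, 21.6% |
| 0.098 each period | 13.4%, 22.4% | 23.3%, 43.7% |

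A repeat run put the recurring Day 0 case as low as 22%, hence the rounded range of 22% to 44%.

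**5. Reading (b): test on CBD-minus-control differences of deltas.**
- Day 0 reference: CBD first gives d - Ld + p1 - p2, and control first gives d + p2 - p1. The mean is **d(1 - L/2)**: d at L = 0, 0.75d at L = 0.5, 0.5d at L = 1.
- Day 14 reference: CBD first gives 2d - Ld + 2p1 - p2, and control first gives d + p2 - 2p1. The mean is **d(1.5 - 0.5L)**: 1.5d at L = 0, d at L = 1.
- Error variance, with s² the within-subject variance and independent visits: Y14 - Y28 has 2s². The Day 14 version is 2·Y14 - Y0 - Y28, with (4 + 1 + 1)s² = 6s², three times as much.

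Period effects cancel with equal sequences, and simulated type I error is about 5% or lower with either reference.

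**6. The proposed contrast.** A rank-sum test of Y14 - Y28 between sequences rejected in 4.6% to 5.3% of null simulations. The estimate is half the shift between sequences. At d = 0.5:

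| L | Estimate | Power, correlation 0 | Power, correlation 0.5 |
|---|---|---|---|
| 0 | 0.50 | 0.99 | 1.00 |
| 0.5 | 0.38 | 0.89 | 0.995 |
| 1 | 0.25 | 0.56 | 0.86 |

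**The case against.** The strongest reply is that the documents, read together, already point to a sound analysis. Section 4 speaks of change from baseline, Section 9.1 lists Day 14 separately from Baseline, and the schedule gives Day 14 no baseline label. The first sentence of 11.1 promises a comparison within subjects because of the crossover, so applying the signed-rank test to paired CBD-minus-control differences is a natural reading. Scores after a two-week condition fit Days 14 and 28 better than Days 7 and 21. Most of this stands. Day 0 is the better-supported reference, and the signed-rank test is not wrong in itself. But 11.1 states none of it, and its wording also fits a test of the CBD change alone.

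The false-positive rates can also be challenged. The 9.8% is a pain-score change in another condition, placed on a scale that Section 11.2 does not define, while the endpoints include strength and range of motion. That stands too. The rates illustrate what reading (a) would do; they do not predict this trial's error rate.

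Finally, the remedy does not remove carryover, and at L = 1 with correlation 0 the Day 14 between-sequence comparison has more power (0.87 unadjusted) than the crossover contrast (0.56). That is true, but the order reverses at L = 0 (0.87 against 0.99), and L is unknown.

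A reader might infer that the CBD effect will be overstated by half, that the trial has no controlled comparison, or that carryover is present. The documents support none of these. The 1.5d figure needs a reference that they disfavour, a comparison is promised though not specified, and they say nothing on how long the effect lasts.

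**Conclusion.** The point holds as a gap in specification that should be fixed. The absence of a washout is certain from the day count. So is the absence from 11.1 of a defined contrast, a period-2 reference and any handling of period or carryover.

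The size is conditional, and the two sets of figures belong to different readings and cannot both apply. Under (a), false positives are about 13% to 22% (Day 14 reference) or 22% to 44% (Day 0 reference) if a 0.098 change recurs each period, and about 7% to 9% or 14% to 22% if it occurs once. The 1.5d result does not arise there: without period effects both references give d. Under (b), type I error is sound, and the risk is an estimate of 1.5d with three times the error variance if Day 14 were used and there were no carryover. With Day 0 the estimate is d(1 - L/2), between d and 0.5d. All of this assumes equal sequences, end-of-period scores, full effect by the end of the CBD period and, for the rejection rates, a 0.5 SD scale with correlation 0 to 0.5.

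**What to change.** Amend Section 11.1 to state four things.
1. The efficacy test is the within-subject CBD-versus-control comparison of end-of-period scores, Day 14 against Day 28, allowing for period. One option is a rank-sum test of the Day 14 minus Day 28 difference between sequences, with half the Hodges-Lehmann shift as the estimate. A signed-rank test on the paired CBD-minus-control difference is an acceptable alternative in balanced sequences, slightly conservative under a period trend.
2. Day 0 is the only baseline for change scores. It cancels from the contrast in item 1 but governs every reported change.
3. The Day 14 between-sequence comparison adjusted for Day 0 is reported as a sensitivity estimate free of carryover.
4. With no washout, the crossover estimate is biased toward no effect if CBD's effect lasts to Day 28.

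The cost is wording only, with no added visits or subjects. Days 7 and 21 become descriptive. Carryover is disclosed rather than removed, and comparing the two estimates will seldom reveal it: at d = 0.5 and correlation 0, power for that comparison is about 0.19 at L = 0.5 and 0.58 at L = 1. The plan should therefore not treat their agreement as proof that carryover is absent.

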5.2 Justification for Dose

Nitecka-Buchta *et al.* performed a double-blind randomized controlled trial of topical CBD for 60 total patients with myofascial pain. Topical application of 67 mg CBD – including other minor cannabinoids – was applied to masseter muscles twice daily for 14 days in the case group. Visual Analog Scores (VAS) were reduced from 5.6 on Day 0 to 1.7 on Day 14 (70.2% reduction) in the case group, versus 5.1 on Day 0 and 4.6 on Day 14 (9.8% reduction) in the control group ($p = 0.00$). (4)

Xu *et al.* performed a randomized controlled trial with cross-over for topical CBD treatment of 29 patients with symptomatic lower extremity neuropathy. Topical application of 250 mg of pure CBD (case arm) was applied up to four (4) times daily for four (4) weeks, and then patients switched to emu oil (control arm) with the same application for 4 weeks followed by cross-over. They showed a statistically significant reduction in Neuropathic Pain Scale scores for intense (5.11 to 4.02) ($p=0.009$) and sharp (4.01 to 3.09) ($p<0.001$) pain between case and control arms. (5)

No side effects or adverse events were noted in either clinical trial.

5.3 End of Study Definition

Primary completion date is the date that the final participant was examined or received an intervention for the purposes of final collection of data for the primary outcome, whether the clinical study concluded according to the pre-specified protocol or was terminated. In the case of clinical studies with more than one primary outcome measure with different completion dates, this term refers to the date on which data collection is completed for all of the primary outcomes defined as the final date for the collection of data for the primary endpoint.

Study completion date is the date the final participant was examined or received an intervention for purposes of final collection of data for the primary and secondary outcome measures and adverse events (for example, last participant's last visit), whether the clinical study concluded according to the pre-specified protocol or was terminated.

6 STUDY POPULATION

6.1 Inclusion Criteria

In order to be eligible to participate in this study, an individual must meet all of the following criteria:

1. Provision of signed and dated informed consent form.
2. Stated willingness to comply with all study procedures and availability for the duration of the study.
3. Male or female, aged 18 years or older.
4. Females of childbearing potential must have a negative urine and blood pregnancy test at Screening and a negative urine pregnancy test before study drug is administered. Females must abstain from sex or use a highly effective method of contraception during the period from Screening to administration of study drug and for 30 days after the last dose of study medication. Standard acceptable methods include abstinence or the use of a highly effective method of contraception, including; hormonal contraception, diaphragm, cervical cap, vaginal sponge, condom with spermicide, vasectomy, intrauterine device. If females are of non-child bearing potential, they must be post-menopausal defined as: age > 55 with no menses within the past 12 months, or history of hysterectomy, or history of bilateral oophorectomy, or bilateral tubal ligation.
5. Males must consent to use a medically acceptable method of contraception throughout the entire study period and for 90 days after their last study drug application. They must agree to not donate sperm for 90 days after their last study drug application.
6. Presence of radiographically confirmed diagnosis of thumb basal joint arthritis.

6.2 Exclusion Criteria

An individual who meets any of the following criteria will be excluded from participation in this study:

1. Subject does not speak English.
2. Subject is blind.
3. Severe cardiac, pulmonary, liver and /or renal disease.
4. Coumadin use at time of screening.
5. History of mental illness.
6. Subjects who are incarcerated.
7. History of drug or substance abuse.
8. Pre-existing CBD or hemp based product usage.
9. Subject has had a corticosteroid injection \leq 3 months prior.
10. Subject has had prior surgery for osteoarthritis treatment.
11. Females who are pregnant, nursing or planning a pregnancy; females of childbearing potential who are unwilling or unable to use an acceptable method of contraception as outlined in this protocol from Screening to the first dose of study medication and for 30 days after the last dose of study medication. Standard acceptable methods include abstinence or the use of a highly effective method of contraception, including; hormonal contraception, diaphragm, cervical cap, vaginal sponge, condom with spermicide, vasectomy, intrauterine device.
12. Any skin disease or condition, including eczema, psoriasis, melanoma, acne or contact dermatitis, scarring, imperfections, lesions, tattoos or discoloration that may affect treatment application, application site assessments, or affect absorption of the study drug.
13. Subjects with ALT/AST >3 times the upper limit of normal at screening.
14. Subjects with history of or active depression or suicide ideation based on Columbia-Suicide Severity Rating Scale (C-SSRS).

15. Subjects taking prescription or non-prescription medication which are substrates of CYP3A4 (Itraconazole, Ketoconazole, Azamulin, Troleandomycin, Verapamil, John's wart, Phenobarbital), CYP2C19 (Nootkatone, Ticlopidine, Rifampin, Omeprazole), CYP2C8 (Montelukast, Quercetin, Phenelzine, Rifampin, Clopidogrel), CYP2C9 (Sulfaphenazole, Tienilic acid, Carbamazepine, Apalutamide, Fluconazole, Celecoxib), CYP1A2 (alpha-Naphthoflavone, Furaflavine, Phenytoin, Rifampin, Ritonavir, smoking, Teriflunomide, Ciprofloxacin, oral contraceptives, Alloprinol) and CYP2B6 (Sertraline, Phencyclidine, Thiotepa, Ticlopidine, Carbamazepine, Efavirene, Rifampin, Bupropion) within 14 days of the study procedure.

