8.2 Participant Discontinuation/Withdrawal

Participants are free to withdraw from participation in the study at any time upon request.

A participant's study treatment would be discontinued for the following reasons:

- Significant study intervention non-compliance
- If any clinical adverse event (AE), laboratory abnormality, or other medical condition or situation occurs such that continued participation in the study would not be in the best interest of the participant
- Disease progression which requires discontinuation of the study intervention
- If the participant meets an exclusion criterion (either newly developed or not previously recognized) that precludes further study participation
- Participant decision to withdraw from study treatment and/or the study.

The reason for participant discontinuation or withdrawal from study treatment will be recorded. Participants who sign the informed consent form and are randomized but do not receive the study intervention may be replaced. Participants who sign the informed consent form, and are randomized and receive the study intervention, and subsequently withdraw, or are withdrawn or discontinued from the study, will not be replaced.

Participants that withdraw from the study (not only from study treatment, but all study follow-up) will not be contacted for any further study visits.

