9.2 Safety Assessments

Medical History: Relevant medical history, including history of mental illness, drug or substance abuse, history of hemp-based product usage and other pertinent history will be recorded in the case report form.

Laboratory Testing: At baseline and Study Day 35, blood draws will be performed on all subjects at the UVA Medical Laboratory. The following tests will be ordered and monitored for clinical abnormalities:

- CBC
- Basic metabolic panel (i.e., BUN, creatinine, CO₂, Cl, K, Na, and glucose)
- Hepatic function testing (i.e., serum transaminases [ALT/AST], total bilirubin, and alkaline phosphatase)
- Pregnancy Testing (if applicable) (Screening)
- Urine Pregnancy Test (if applicable) (Screening and Day 0 before dosing)

Daily Skin Monitoring: Subjects will be asked to observe the testing site for physiologic changes, skin changes or other adverse events daily. Subjects will be provided with a daily diary to record and monitor any observed changes. The daily diary is provided in Appendix 14.3. They will be instructed to notify the investigator of any sudden changes in skin appearance or increase in their arthritic symptoms that are more than minimally tolerated.

Physician Skin Monitoring: At baseline and at every subsequent visit, the investigator will assess the CBD cream site for adverse events. A score will be given corresponding to the assessment tool below:

Score	Definition
0	No erythema
1	Minimal erythema
2	Moderate erythema with sharply defined borders
3	Intense erythema with or without edema
4	Intense erythema with edema and blistering/erosion

- NOTE: Changes in skin appearance will be evaluated using the standardized skin assessment tool above. A patient will be removed from study with a score ≥ 2 .

Clinical Evaluations: Subjects will be monitored weekly for the following:

- Vital sign assessments (i.e., heart rate and blood pressure)
- Suicidal behavior and thoughts as a specific question using the Columbia-Suicide Severity Rating Scale (C-SSRS). The full questionnaire is provided in Attachment 3 (Appendix 14.4).
 - Monitor for somnolence and sedation and advise patients not to drive or operate machinery until they have gained sufficient experience on study drug. Subjects will be asked if they feel more, less, or no change in their level of fatigue during the time they were administering study drug.

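### Exclusion 11 requires female contraception before the first dose and after the last dose but not during the 28 days of dosing; inclusion 4 and section 6.4 do not clearly fill the gap.

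*Combined protocol and SAP*

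**What the plan says.** The protocol states the female contraception requirement in three places.

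- Section 6.2, exclusion 11, excludes women of childbearing potential who will not or cannot use contraception "from Screening to the first dose of study medication and for 30 days after the last dose of study medication". It also bars "Females who are pregnant, nursing or planning a pregnancy".
- Section 6.1, inclusion 4, requires abstinence or contraception "during the period from Screening to administration of study drug and for 30 days after the last dose of study medication".
- Section 6.4 repeats the inclusion 4 wording as a rule for conduct during the trial.

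The rule for men, in inclusion 5 and again in section 6.4, is different. They must use "a medically acceptable method of contraception throughout the entire study period" and for 90 days afterwards.

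Section 8.2 lists among the reasons for stopping treatment: "If the participant meets an exclusion criterion (either newly developed or not previously recognized) that precludes further study participation". Sections 9.2 and 14.1 schedule a urine pregnancy test at screening and on Day 0 before dosing, and a blood pregnancy test at screening only.

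**The concern.** A contraception rule in a drug trial exists mainly to cover exposure. Read literally, exclusion 11 covers the run-in and the follow-up but not the exposure. A woman who agreed to contraception before the first application and after the last one, but declined it in between, would not be excluded by this criterion. The two companion clauses do not clearly exclude her either.

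What is at stake is participant safety and consistent application of eligibility, not the efficacy comparison. A pregnancy beginning during dosing would not be picked up by any scheduled test, because none is planned after Day 0. It could come to light only if the participant reported it, for example at one of the Day 7 to Day 35 visits.

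**Working it through.** **Reading the clauses side by side**

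| Clause | Before dosing | During dosing | After dosing |
|---|---|---|---|
| Exclusion 11 (women) | Named, ends at first dose | Not named | 30 days |
| Inclusion 4 and section 6.4 (women) | Named, ends at administration of the drug | Unclear | 30 days |
| Inclusion 5 and section 6.4 (men) | Named | Named | 90 days |

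In inclusion 4 and section 6.4, administration could mean the first dose or the whole four weeks. Two features of the text favour the first dose. Inclusion 4 itself times the second urine pregnancy test by reference to the drug being administered, and there it can only mean the first application. Exclusion 11 restates what appears to be the same window and ends its first part at the first dose. These features make the narrower reading the more natural one, but they do not settle it.

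**Inputs**

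- Screening: up to 7 days before Day 0 (section 14.1).
- Dosing: participants are "assigned two (2) weeks of the case or control topical cream and then crossover to the other cream for two (2) more weeks" (section 5.1), so 2 × 14 = 28 days. The supply agrees: 28 mL ÷ 2 mL per day = 14 days per condition (section 7.2).
- CBD dose: "the cream will be formulated to deliver approximately 12.4 mg of purified CBD per day" (section 7.2), from two 1 mL applications at 6.2 mg/mL.
- Follow-up cover: 30 days after the last dose.
- Visit window: ±1 day (section 14.1).
- Allocation: 1:1 (section 11.2.1).

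**Days named and omitted by exclusion 11**

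- Full span with screening at Day -7: 7 + 28 + 30 = 65 days.
- Named: 7 + 30 = 37 days.
- Omitted: 65 − 37 = 28 days, and 28/65 = 43%.
- With screening close to Day 0 the span is 28 + 30 = 58 days, and 28/58 = 48%.

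**What falls in the omitted days**

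- CBD: 14 days × 2 = 28 applications; 28 × 1 mL × 6.2 mg/mL = 173.6 mg.
- Shea butter alone: 14 days × 2 = 28 applications.

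**Last scheduled pregnancy test to first CBD**

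- CBD-first sequence: Day 0 to Day 0, so 0 days.
- Control-first sequence: Day 0 to Day 14, so 14 days (13 to 15 with the visit window). Under 1:1 allocation this applies to about half of the women, and those two weeks lie wholly inside the period exclusion 11 leaves out.

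**The case against.** The strongest reply is that exclusion 11 should not be read alone. A participant must meet every inclusion criterion, exclusion 11 refers to contraception as the protocol sets it out, and if administration in inclusion 4 means the four-week course, a woman declining contraception during dosing already fails inclusion 4. A 30-day tail also makes little sense unless cover is continuous. This is good evidence of intent. It does not repair the text, because inclusion 4 does not say that it covers the course.

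A second reply is that the scenario is unlikely: few women would use contraception before and after dosing but not during it, and women planning a pregnancy are excluded. It is indeed unlikely for an intrauterine device, hormonal contraception or vasectomy. It is less so for the on-demand methods the protocol also accepts, such as condom with spermicide, diaphragm, cervical cap, sponge or abstinence. The planning bar does not reach a woman who has no such plan and uses no contraception. The stopping rule in section 8.2 acts only once a pregnancy is known.

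Third, the percentages count days in a sentence and do not measure risk. Half the omitted days are on shea butter alone, and the number of women of childbearing potential could be small. That is right, and the figures should be read only as the extent of the omission.

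Fourth, the absence of a pregnancy test after Day 0 would remain after the edit. This is also right. It is context for why the wording matters, and the edit does not claim to cure it.

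**Conclusion.** The concern holds. Exclusion 11 as written omits the 28-day dosing period, 43% to 48% of the span a continuous rule would cover, and the omission includes all CBD exposure. Inclusion 4 and section 6.4 are ambiguous on the same point. The protocol covers dosing explicitly for men and not for women, so this is an inconsistency within the document and not a matter of preference.

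The day counts assume screening between Day -7 and Day 0 and a last dose at about Day 28. The conclusion concerns the protocol wording only. The consent form was not reviewed and may state the requirement in full, but it would not correct the eligibility text. No participant-level risk can be calculated, since the number of women of childbearing potential is not given. Sample size, power and analysis are unaffected. The sponsor should correct the wording.

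**What to change.** In exclusion 11, inclusion 4 and section 6.4, replace the two-part window with a single continuous one: *from Screening, throughout the entire study treatment period, and until 30 days after the final application*. This brings the female criterion into the same form as the male one. The consent form should be checked so that it says the same.

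The cost is one phrase in three places, with no new visit, test or analysis.
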